# 7.0 STATISTICAL CONSIDERATIONS

#### 7.1 Sample Size and Accrual

We will enroll 25 adult subjects with suspected with suspected kidney cancer and planned surgical nephrectomy. We have deep recruitment experience for kidney CEUS imaging. Approximately 150 nephrectomies for localized disease are performed at UNC yearly. Based on our previous recruitment rate of ~75% and a strong partnership with our urology colleagues, we anticipate no problems meeting our recruitment goal of 25 subjects.

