#### 7.1.1 Primary Objective

# 7.1.1.1 Predicting kidney mass diagnosis using 3D CEUS generated metrics.

The proposed sample of 25, assuming 60% clear cell legions, achieves 63.2% power to detect a difference of 0.1000 between a diagnostic test with an area under the ROC curve (AUC) of 0.8000 and another diagnostic test with an AUC of 0.9000 using a two-sided z-test at a significance level of 0.050. The correlation between the two diagnostic tests is assumed to be 0.9 for the positive group and 0.9 for the negative group.

The proposed sample of 25, assuming 60% clear cell legions, achieves 88.7% power to detect a difference of 0.1500 between a diagnostic test with an area under the ROC curve (AUC) of 0.8000 and another diagnostic test with an AUC of 0.9500 using a two-sided z-test at a significance level of 0.050. The correlation between the two diagnostic tests is assumed to be 0.9 for the positive group and 0.9 for the negative group.

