# 7.2.2 Comparing diagnostic accuracy of F-R infusion imaging technique to low MI bolus imaging technique.

Image Analysis (Flash-Replenishment TIC analysis): For each 0.5-1 cm step, we will produce a TIC by delineating an ROI of the entire mass and measuring the mean contrast signal intensity over the time course of the F-R. We will model TIC using a mono-exponential equation, UI=A(1 -  $e^{-\beta t}$ ), where UI is ultrasound intensity and  $\beta$ , the slope of the tangent to the curve, represents the rate of perfusion. The height of the curve, A, represents the perfusion volume. To produce a single value for  $\beta$  for the entire tumor volume, we will calculate a weighted average based on the ROI area of the mass at each step. This value will serve as the WI rate.

Gold Standard Comparator: Histologic diagnosis from pathologic tissue.

*Statistical Analysis:* We will follow the model building and evaluation strategy used for the primary objective. This will be done separately for bolus and infusion imaging modalities, as well as combining the two multiparametric scores. We will compare AUCs from final logistic regression models obtained for bolus and infusion using a Z-test at alpha=0.05, with standard errors obtained by bootstrapping correctly adjusting for the fact that the two AUCs are calculated using the same data and hence correlated. We will conduct similar tests comparing the AUC based on the combined model to those based on bolus and infusion multiparametric scores separately. The proposed tests with sample size 25 have 80% power to detect a difference of .1 in the AUCs (0.8 vs 0.9) and 90% power to detect a difference of 0.15 (0.8 vs 0.95).

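### In 7.2.2 the combined-versus-single-technique comparisons are AUC Z-tests between nested models on the same 25 patients: far below the 5% level with no gain, and usually missing a gain of the planned size

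*Combined protocol and SAP*

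**What the plan says.** Section 7.2.2 applies the model-building strategy of 7.2.1 to bolus and infusion separately, "as well as combining the two multiparametric scores". The technique comparison is specified as follows: "We will compare AUCs from final logistic regression models obtained for bolus and infusion using a Z-test at alpha=0.05". Its variance is to come from a bootstrap meant to allow for the dependence between two AUCs estimated on one set of patients. The same approach is then extended: "We will conduct similar tests comparing the AUC based on the combined model to those based on bolus and infusion multiparametric scores separately".

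The section closes with a power statement that does not separate these comparisons: "The proposed tests with sample size 25 have 80% power to detect a difference of .1 in the AUCs (0.8 vs 0.9", and 90% for 0.8 versus 0.95. For the bolus-versus-infusion objective, 7.1.2.1 gives 63.2% and 88.7% for the same two differences.

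Section 7.2.2 does not mention nesting, state whether the test is one- or two-sided, or say whether models are refitted within each bootstrap resample. Section 7.2.1 plans tests of individual logistic coefficients, but 7.2.2 does not name them for the combined-versus-single question.

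**The concern.** The combined model takes the bolus and infusion scores together, so the bolus model is the combined model with zero weight on infusion, and the reverse. If the second technique adds nothing, its fitted weight is near zero and both models rank patients almost identically. AUC depends only on ranks, so the estimated difference is close to zero and skewed. Divided by its standard error it is not a standard normal variable. Allowing for correlation between the two AUCs corrects the variance but not the shape of this null distribution.

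At stake is whether the study can recognise added value from using both techniques. A non-significant result, read beside a stated power of 80% or 90%, would look like evidence that the second technique adds nothing.

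**Working it through.** **1. Inputs from the document.** "We will enroll 25 adult subjects" (7.1). The split is 15 clear cell and 10 not, from "assuming 60% clear cell legions" (7.1.1.1). The power calculation there is made "using a two-sided z-test at a significance level of 0.050", with a correlation of 0.9 in each group. Targets are AUC 0.80 versus 0.90 and 0.80 versus 0.95.

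**2. The plan's own power figures.** For two fixed scores, power = Φ((d − z·SE0)/SE1), with the Hanley-McNeil variance V(A) = [A(1−A) + (m−1)(q₁−A²) + (n−1)(q₂−A²)]/(mn), where q₁ = A/(2−A) and q₂ = 2A²/(1+A). With m=15 and n=10:
- V(0.80) = 0.007822 and V(0.90) = 0.003922.
- SE0 = √(2 × 0.007822 × 0.1) = 0.03955.
- SE1 = √(0.007822 + 0.003922 − 2 × 0.9 × 0.08844 × 0.06262) = 0.04213.
- Two-sided power = Φ((0.1 − 1.96 × 0.03955)/0.04213) = Φ(0.53) = 70.3%. For 0.80 versus 0.95 it is 91.6%.
- One-sided: 79.7% and 94.7%.

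Swapping the group roles gives 63.5% and 88.2% two-sided; a binormal variance gives 65.2% and 87.5%. So 63.2% and 88.7% reproduce within 2 points. No single variant tried gives both 80% and 90%. All of these formulas assume two pre-specified, non-nested scores.

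**3. Simulating the nested comparison.** Assumptions not in the document: independent normal markers with unit variance. The bolus shift is √2·Φ⁻¹(0.80) = 1.190. Combined AUCs of 0.90 and 0.95 need total shifts of 1.812 and 2.326, so the infusion marker has shift √(1.812² − 1.190²) = 1.367 or √(2.326² − 1.190²) = 1.999. Rejection rates at n=25, two-sided 5% (400 trials per setting for the refit bootstrap):

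| Bolus + infusion terms | True AUC, bolus → combined | Z, fixed-score SE | Z, refit bootstrap SE | LR test, chi-square reference |
|---|---|---|---|---|
| 1+1 | 0.80 → 0.80 | 0.1% | 0.5% | 6.7% |
| 1+1 | 0.80 → 0.90 | 14.1% | 16.5% | 80.6% |
| 1+1 | 0.80 → 0.95 | 31.8% | 30.7% | 96.6% |
| 2+1 | 0.80 → 0.80 | 0.2% | 0.5% | 9.6% |
| 2+1 | 0.80 → 0.90 | 11.6% | 16.5% | 78.8% |
| 2+1 | 0.80 → 0.95 | 27.6% | 37.0% | 96.1% |
| 3+2 | 0.80 → 0.80 | 0.4% | 2.5% | 15.5% |
| 3+2 | 0.80 → 0.90 | 15.7% | 21.5% | 75.1% |
| 3+2 | 0.80 → 0.95 | 28.5% | 45.0% | 93.6% |

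Across these and further runs with stacked scores or AUC-selected subsets, power is about 4–22% for the 0.10 gain and 13–45% for the 0.15 gain.

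**4. A fair comparator.** The chi-square reference is liberal here, so its power flatters the LR test. Further one-marker runs took the critical value from simulated null trials (4.68 to 5.06, instead of 3.84). The LR test then has 69–76% power for 0.90 and 94–96% for 0.95. A true permutation version gave 68% and 93% (150 runs only). In one-marker runs with within-group correlation 0 to 0.9, the Z-test had 12–14% and 31–34%; another refit-bootstrap run gave 17% and 37%. Tested one-sided, the Z-test has about 28% and 55% power, and about 0.7% rejection with no gain.

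**5. Separating the causes.** Two non-nested fixed scores with the same correlation as the nested pair (1.190/1.812 = 0.66; 1.190/2.326 = 0.51) give the Z-test only 17% and 35% power. At a score correlation of 0.9 it has 33% and 59%. Nesting therefore costs only a few points of power. The level is another matter: non-nested scores with equal AUCs reject in 2.1% (correlation 0.9) or 3.8% (0.5) of trials, against 0.1% for the nested pair. At n=100 the nested Z-test still rejects in 0.1% with no gain but has 90% power for the 0.10 gain. The wrong level is structural; the low power is mostly sample size and the choice of an AUC difference.

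**6. Bolus versus infusion.** If both models share B-mode or patient terms and the technique-specific terms add nothing, the Z-test between them rejects in 0.2% of 2,000 trials: the same degeneracy.

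**The case against.** The strongest case on the other side has four parts.

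- **The simulation is simpler than the plan.** Section 7.2.1 lists 12 candidate factors with AUC-based selection, so a selected combined model need not contain the selected single-technique model. This stands as a qualification. But the runs with AUC-selected subsets gave no rejections with no gain, and about 4% and 15% power, so selection does not rescue the test.
- **Coefficient tests are already planned in 7.2.1.** They offer a possible route to added value. But 7.2.2 does not assign them to this question, and the Z-tests it does name would remain.
- **Sidedness is open.** A one-sided test roughly doubles power, to 28% and 55%. That is still far below 80% and 90%.
- **It is a secondary comparison and the error is conservative.** The stated objective is bolus versus infusion; combined versus single is an addition with no decision rule attached. This stands and limits the severity.

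A reader might infer more than the documents support. One inference is that the test almost never rejects whatever the truth; that describes the no-gain case only. Another is that nesting causes the missed gains; step 5 shows that it does not, for the most part. A third is that bolus versus infusion is free of the problem; that depends on which terms the two models share.

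**Conclusion.** The point holds in a limited form. For combined versus bolus and combined versus infusion, the planned Z-test does not have its nominal 5% level: with no gain it rejects in about 0–2.5% of trials, depending on the standard error and the number of terms. At the plan's own targets it would usually, not always, miss a real gain, while a calibrated likelihood-ratio test would find most such gains in the same data. The power stated in 7.2.2 does not apply to these comparisons.

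The power figures rest on assumed normal markers, a 15/10 split and a single-technique AUC of 0.80. The level failure persists across the numbers of terms, standard errors and sample sizes examined, provided the models are nested or nearly so. This should be fixed, but it affects neither the primary analysis nor safety.

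**What to change.** In 7.2.2:

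1. Replace the two combined-versus-single Z-tests with a test of the added technique's term or terms in the combined logistic model. Use a likelihood-ratio statistic with a permutation reference, or a penalised likelihood-ratio test, on pre-fixed metrics or out-of-fold scores. Do not use the plain chi-square reference: at n=25 its level is about 7–8% with one term added to a one-term model, and 15.5% in the 3+2 setting.
2. Report the AUC gain, corrected for optimism, as an estimate with an interval. The correction matters: with 3+2 terms and no true gain, the apparent AUC moves from 0.840 to 0.877.
3. State that the power figures do not apply to combined versus single. For bolus versus infusion, reconcile 80% and 90% with the 63.2% and 88.7% in 7.1.2.1. Merely restricting the existing sentence to that comparison would keep a figure that 7.1.2.1 contradicts.
4. Keep the Z-test for bolus versus infusion only if the two scores compared are technique-specific, and state whether it is one- or two-sided.

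The cost is SAP wording and a few lines of code. No further patients or imaging are needed.

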#### 7.1.2 Secondary Objectives

# 7.1.2.1 To compare diagnostic accuracy of F-R infusion imaging technique to low MI bolus imaging technique.

The proposed tests with sample size 25 have 63.2% power to detect a difference of 0.1 in the AUCs (.8 vs .9) and 88.7% power to detect a difference of 0.15 (0.8 vs 0.95).

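### Sections 7.1.2.1 and 7.2.2 give 63.2% and 80% power for the same bolus-versus-infusion comparison, and 7.2.2 does not state the inputs behind its figure

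*Combined protocol and SAP*

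**What the plan says.** Comparing the two imaging techniques is secondary objective 2.2.1. Its power is stated twice.

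- Section 7.1.2.1 (sample size): "The proposed tests with sample size 25 have 63.2% power to detect a difference of 0.1 in the AUCs (.8 vs .9", and 88.7% for 0.8 vs 0.95.
- Section 7.2.2 (analysis plan): "The proposed tests with sample size 25 have 80% power to detect a difference of .1 in the AUCs (0.8 vs 0.9", and 90% for 0.8 vs 0.95.

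The test in 7.2.2 is described as follows: "We will compare AUCs from final logistic regression models obtained for bolus and infusion using a Z-test at alpha=0.05", with bootstrap standard errors that allow for the correlation between the AUCs. Two further tests follow: "We will conduct similar tests comparing the AUC based on the combined model to those based on bolus and infusion multiparametric scores separately". Section 7.2.2 gives n, the AUC pairs, the type of test and alpha. It does not give the clear cell share, the value of the correlation, or whether the test is one- or two-sided.

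Section 7.1.2.1 does not restate those three inputs either, but its two figures equal those of section 7.1.1.1, which does: "The proposed sample of 25, assuming 60% clear cell legions, achieves 63.2% power to detect a difference of 0.1000", "using a two-sided z-test at a significance level of 0.050", and "The correlation between the two diagnostic tests is assumed to be 0.9 for the positive group and 0.9 for the negative group".

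**The concern.** Two nearly identical sentences give different power for one comparison. Section 7.2.2 refers to three Z-tests, but bolus versus infusion is one of them and is the only comparison in 7.1.2.1, so the 80% is claimed for it too.

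The two sections imply different chances of missing a true AUC difference of 0.1: 100 − 63.2 = 36.8% and 100 − 80 = 20%. Someone interpreting a non-significant result from the analysis section would see a conventional 80% and could take the techniques to be similar. If the test is two-sided, as in 7.1.1.1, the only calculation in the protocol with stated inputs does not support that much confidence.

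**Working it through.** **Inputs (section 7.1.1.1).** n = 25 with 60% clear cell, so 15 clear cell and 10 non-clear cell; correlation 0.9 in each group; alpha 0.05 two-sided (z = 1.960). For a one-sided test z = 1.645. AUC 0.8 against 0.9 (Δ = 0.10) or 0.95 (Δ = 0.15).

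**Formula.** Power = Φ[(Δ − z·SE0)/SE1], where SE1 is the standard error of the AUC difference under the alternative and SE0 the one used for the critical value. The protocol names no variance formula, so I tried three choices of SE0: (a) equal to SE1, (b) both AUCs at 0.8, (c) both AUCs at their average.

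Hanley-McNeil variance: V(θ) = [θ(1−θ) + (n₊−1)(Q1−θ²) + (n₋−1)(Q2−θ²)]/(n₊n₋), with Q1 = θ/(2−θ) and Q2 = 2θ²/(1+θ). The variance of the difference is V₁ + V₂ − 2(0.9)√(V₁V₂). The large-sample version is V(θ) = (Q1−θ²)/n₋ + (Q2−θ²)/n₊. The Obuchowski-McClish binormal variance applies the 0.9 to the underlying scores instead of the AUCs.

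**Step 1: the protocol's 63.2%/88.7%.** The protocol does not say which group counts as positive. Hanley-McNeil, choice (b), with 10 positive and 15 negative:

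- V(0.8) = 0.009304, V(0.9) = 0.005070, V(0.95) = 0.002612.
- SE0 = √(2 × 0.009304 × 0.1) = 0.04314. SE1 = 0.04485 for 0.9 and 0.05516 for 0.95.
- Δ = 0.10: Φ[(0.10 − 1.960 × 0.04314)/0.04485] = Φ(0.344) = 63.5%.
- Δ = 0.15: Φ[(0.15 − 1.960 × 0.04314)/0.05516] = Φ(1.187) = 88.2%.

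Both are within 0.5 points. Obuchowski-McClish with choice (b) gives 65.2%/87.5%, within 2 points.

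**Step 2: can 80%/90% be reached?** Each cell shows power in % for 0.8 vs 0.9 / 0.8 vs 0.95, with 15 positive, 10 negative and correlation 0.9.

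| Variance | Sides | (a) | (b) | (c) |
|---|---|---|---|---|
| Hanley-McNeil | 2 | 66.1/81.3 | 70.3/91.6 | 78.0/95.4 |
| Hanley-McNeil, large-sample | 2 | 68.0/82.8 | 72.5/92.6 | 80.0/96.0 |
| Obuchowski-McClish | 2 | 57.8/71.8 | 65.2/87.5 | 72.3/92.1 |
| Hanley-McNeil | 1 | 76.7/88.6 | 79.7/94.7 | 84.9/96.9 |
| Hanley-McNeil, large-sample | 1 | 78.3/89.7 | 81.4/95.4 | 86.3/97.4 |
| Obuchowski-McClish | 1 | 69.6/81.4 | 75.0/91.5 | 80.1/94.5 |

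Two-sided, power for the 0.1 difference runs from 57.8% to 80.0%. The one cell at 80.0% carries 96.0% for the 0.15 difference, so no two-sided cell gives the stated pair. The nearest cell of all is one-sided: 78.3%/89.7%.

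**Step 3: does sidedness alone reconcile the sections?** No. Converting 63.2% directly: its normal quantile is 0.337, and 0.337 + 1.960 − 1.645 = 0.652, which gives 74.3%. The same conversion takes 88.7% to 93.6%. The formula behind 78.3%/89.7% gives 68.0%/82.8% two-sided, not 63.2%/88.7%. A one-sided origin would therefore also need a different variance formula.

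**Step 4: correlation.** Raising it to 0.94, two-sided (Obuchowski-McClish, choice (b)), gives 81.4%/93.7%, again not the stated pair.

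**The case against.** The strongest reply is that the 80% has not been shown to be a miscalculation. One two-sided variant on the 7.1.1.1 inputs reaches 80.0%, and a one-sided one comes near both figures. Section 7.2.2 also says "We will follow the model building and evaluation strategy used for the primary objective", and the primary objective's test in 7.2.1 is one-sided, so the two sections may describe different tests.

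The first part stands: the recalculation does not show which figure is in error. The one-sided reading remains only a possibility. The test in 7.2.1 sets one model's AUC against a fixed 0.8, whereas 7.2.2 specifies its paired comparison separately, and step 3 shows that sidedness alone is not enough. If that reading were right, the two sections would still give power for different tests without saying so.

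It is also fair to say that the consequence is modest. The objective is secondary, no stopping or success rule uses the figure, the sample-size section itself carries the less favourable 63.2%, and a null result should be read mainly from the estimated difference and its standard error. This limits the weight of the point but does not remove the contradiction.

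**Conclusion.** The concern holds. Two current sections contradict each other on the power of one comparison: 63.2% against 80% for AUC 0.8 vs 0.9, a gap of 16.8 points. That conclusion rests on the text alone. The 1.3-point gap for 0.8 vs 0.95 (88.7% against 90%) may be rounding and is not counted.

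The recalculation adds that 63.2%/88.7% is consistent with the inputs in 7.1.1.1, while 80%/90% is not obtained as a pair from any two-sided variant tried. It assumes a 15/10 split, correlation 0.9 and textbook variance formulas. None of these represents the planned bootstrap standard errors on logistic models selected in the same 25 subjects, so every power figure here is nominal. This should be fixed, but it does not threaten the design.

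**What to change.** Re-run the power calculation once and put the same statement in 7.1.2.1 and 7.2.2, for example:

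*Assuming 60% clear cell (15 of 25 subjects, with [clear cell / non-clear cell] as the positive group), a [one-/two-]sided Z-test at alpha = 0.05, a correlation of [r] in each group and [variance formula], power for bolus versus infusion is [x]% for AUC 0.8 vs 0.9 and [y]% for 0.8 vs 0.95.*

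- If the test is two-sided as in 7.1.1.1, replace 80%/90% in 7.2.2 with 63.2%/88.7% once the re-run confirms them.
- If 80%/90% rest on a one-sided test or on other inputs, state these in 7.2.2 and correct 7.1.2.1.
- Say whether the figures also apply to the two comparisons with the combined model, or that no power is claimed for those.

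The cost is one calculation and about one sentence in each section. Sample size and analysis are unchanged. The drawback is that the stated power for this secondary objective may become less favourable.

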#### 7.2.3 Predicting kidney mass stage using 3D CEUS-generated metrics

*Image Eligibility:* CEUS mass images from individuals with clinical stage T2a or lower tumors will be eligible for this sub-analysis. We estimate that 15 tumors will meet these criteria since over 50% of kidney cancer resections at UNC are for T2a or lower clinical stage tumors.

*Imaging Procedure and Analysis:* We will use Matlab (Mathworks, Natick, MA) to measure WI and WO rates from TIC analyses. We will apply the 3D volume rendering exploratory analyses described in the primary outcome to this outcome measure. Qualitative interpretation of 3D volume renderings will be assessed and compared to the clinical outcome.

*Gold Standard Comparator:* We will compare the gold standard of postsurgical pathologic stage to WI/WO rates generated from CEUS TICs.

Statistical Analysis: We will use the continuous variables of WI and WO to predict the binary outcome measure of pathologic stage T3 disease or greater. We will calculate means (standard deviations) and 95% confidence intervals for WI and WO for those  $\geq$  stage T3 vs. < stage T3, and compare via t-tests at alpha=.05. We will use logistic regression to assess ability of WI and WO to predict stage T3 disease or greater, both separately and together. We will obtain nonparametric estimates of AUC along with 95% confidence intervals for WI alone, WO alone, and WI and WO combined using the fitted logistic regression models. We will also add patient specific factors to the logistic regression models, to assess the added value of the WI and WO measurements, with analyses to include tests of the effect parameters from the fitted logistic regression models and estimates and confidence intervals for AUCs from those models.

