## 4.0 STUDY PLAN

4.1 STUDY SCHEMA

#### 4.2 Study Procedures

#### 4.2.1 Enrollment/Recruitment

We will recruit subjects from UNC urology and urologic oncology clinics. Patients  $\geq$ 18 years of age who have at least one suspected kidney cancer with a solid or partially solid lesion and planned surgical resection will be eligible. Pregnant patients and patients with known adverse microbubble reactions will be excluded. We will approach patients during clinic visits or by telephone and schedule consenting individuals for 3D CEUS within 3 months before planned surgery. If surgery is delayed, lesions will be reimaged prior to surgery to meet the 3-month window. The goal is to minimize changes that may occur in tumor pathology between the time of imaging and time of resection. Subjects may also be asked to return for an additional imaging visit if they are determined to have more than one eligible lesion.

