#### 4.2.2.2 Flash-replenishment infusion imaging

Following low MI bolus imaging, we will use the F-R infusion protocol and infuse diluted microbubbles with a calibrated syringe pump. We will translate the transducer across the mass in 0.5-1 cm steps to image the entire mass, executing a F-R pulse at each step. Imaging time will be 3-15 minutes depending on mass size. We will monitor the subject for adverse

reactions during the procedure. Images will be coded and stored for later analysis.

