#### 4.2.3 Medical Record Abstraction

We will perform chart review to obtain histologic diagnosis of subtype as determined by standard of care pathologic examination. Routine formalin fixed specimens will be examined with standard light microscopy. An experienced UNC pathologist will document size, gross description, and tumor subtype, grade and stage per standard-of-care clinical pathology processes using the American Joint Committee on Cancer TNM staging system and the World Health Organization/International Society of Urologic Pathologists grading system. All pathological studies will be conducted per institutional standards.

	Screening	Pre- CEUS	CEUS study	Early Termination 	Post-CEUS study
Inclusion/	Х				
Exclusion Criteria					
Comprehensive Medical	×	V 2			
History	^	Λ-			
Informed Consent	X1	X 			
Education of potential side		×			
effects		^			
Pregnancy test (urine), if		V 3			
applicable		N			
Contrast-Enhanced US			v		
(CEUS)			^		
AE Assessment			X4	Х	
Review medical record for				v	v
pathology results				^	^

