#### 7.2 Data Analysis Plans

#### 7.2.1 Predicting kidney mass diagnosis using 3D CEUS generated metrics.

*Image Analysis (Low MI TIC analysis):* We will use Matlab (Mathworks, Natick, MA) for time intensity curve (TIC) analysis and 3D volume rendering. For each imaging plane, we will create a region of interest (ROI) by delineating the entire mass in the image slice. We will produce a TIC by taking the mean signal intensity in the ROI at each time point and calculate the metrics of wash-in rate (WI), wash-out rate (WO), mean transit time (MTT), time to peak (TTP) and peak enhancement relative to the surrounding parenchyma (PE) for each x-sweep position. A weighted average based on the ROI area at each position will be used to produce single values for the 3D volume for each TIC metric (WI, WO, MTT, TTP and PE). We will repeat this process for each plane of imaging.

3D volume rendering: We will also create 3D renderings of the tumor vasculature from the CEUS images. We will sort the image data collected over the 3-minute period after a bolus injection by the x- (or y-) sweep position, then by capture time in relation to the start of bolus injection through the wash-out period. We will produce a cumulative contrast image (CCI) at each position with the time-dependent image data by summing all time-dependent image data at each position. The images show where the microbubbles have travelled throughout the acquisition period, and since microbubbles are confined to the vascular spaces, the images provide excellent delineation of the vasculature. We will stack the CCIs together to create a 3D rendering.

Multiparametric score and statistical analysis: We will combine the

Table 1. Factors to be used in multiparametric score					
CEUS factors	B-mode factors	Patient factors			
WI, WO, MTT,	Length,	Age, sex, race			
TTP, PE, total	echogenicity,				
volume	shape				

quantitative data derived from CEUS image analyses into a single score. For the primary analysis using the gold

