standard of histologic diagnosis to differentiate clear cell from non-clear cell tumors, we will use logistic regression to build predictive models based on multiple parameters from CEUS (WI, WO, MTT, TTP, PE and tumor volume), B-mode US images (length, echogenicity, shape), as well as patient factors (age, sex, race) (Table 1). We will assess the effects of individual parameters using hypothesis tests based on parameter estimates from the fitted logistic regression model. This approach facilitates assessment of the added value of the CEUS measurements over other patient factors. We will calculate nonparametric estimates and 95% confidence intervals for area under the curve (AUC) using the fitted logistic regression models, both with and without non-CEUS patient factors. We will use model selection procedures, including AUC, to identify a final model, with a one-sided test of AUC  $\leq .8$  vs AUC  $\geq .8$  at alpha=.05 for the final model. We will use model selection procedures based on optimizing AUC to identify a final model, with a one-sided test of AUC<=0.8 vs AUC>=.8 at alpha=.05 for the final model.

Gold Standard Comparator: Histologic diagnosis from pathologic tissue.

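### Nothing in the plan masks image reading to pathology or fixes image metrics before histology is known, so the AUCs may be biased upward by an unknown amount

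*Combined protocol and SAP*

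**What the plan says.** **Timing of imaging.** Section 4.2.1 has the team "schedule consenting individuals for 3D CEUS within 3 months before planned surgery", and lesions are re-imaged if surgery slips. Acquisition therefore comes before surgical pathology.

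**Timing of reading.** Section 4.2.2.2 says only: "Images will be coded and stored for later analysis". It gives no date, no reader, and no statement that the code hides the pathology result.

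**Reference standard.** Section 4.2.3 states: "We will perform chart review to obtain histologic diagnosis of subtype as determined by standard of care pathologic examination". The time and events table places this review at the post-CEUS (or early termination) column, with no link to image analysis.

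**Steps that involve judgement.**
- Bolus imaging (7.2.1): "we will create a region of interest (ROI) by delineating the entire mass in the image slice". PE is taken relative to nearby parenchyma, with no rule for selecting it.
- Infusion imaging (7.2.2): at each step, "we will produce a TIC by delineating an ROI of the entire mass".
- The primary model (7.2.1) also takes in "B-mode US images (length, echogenicity, shape").
- Stage (7.2.3): "Qualitative interpretation of 3D volume renderings will be assessed and compared to the clinical outcome". No scale or reader is named.

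**Data access.** Section 8.3 lets study personnel in general enter data in REDCap. It does not separate image readers from pathology data.

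**The concern.** The primary endpoint is the metric or metrics that best predict pathologic diagnosis, judged in 7.2.1 by a one-sided test of AUC against 0.8. If the person placing an ROI border, choosing the comparison parenchyma or grading echogenicity already knows the tumour is clear cell, those choices can drift towards the known answer. The estimated accuracy then partly reflects the reference standard rather than the image.

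Imaging before surgery protects the raw images. It does not protect a reading made later. With 25 subjects, a few influenced readings can matter, and the protection cannot be restored once a reader has seen the pathology.

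**Working it through.** **1. The plan's own figure.** The point rests on no stated number, but the effect the trial is sized on sets the scale. Section 7.1.1.1 gives 63.2% power for AUC 0.80 vs 0.90 and 88.7% for 0.80 vs 0.95, with N = 25, 60% clear cell (15 and 10) and two-sided alpha 0.05.

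Hanley-McNeil variance: V(A) = [A(1−A) + (n1−1)(Q1−A²) + (n0−1)(Q2−A²)]/(n1·n0), with Q1 = A/(2−A) and Q2 = 2A²/(1+A).
- V(0.80) = (0.16 + 14×0.02667 + 9×0.07111)/150 = 0.00782, so SE = 0.0884.
- Paired test: null variance 2V(0.80)(1−r); alternative variance V1 + V2 − 2r√(V1V2).
- With r = 0.88 between the two AUCs, power is 63.2% and 88.6%, which reproduces the plan. This r was backed out and is not stated. Using the plan's 0.9 directly as the AUC correlation gives 70.3% and 91.6%.

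Masking or locking changes none of these figures.

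**2. Which judgement reaches which result.**

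| Step | Feeds | Enters an AUC? |
|---|---|---|
| Bolus delineation | WI, WO, MTT, TTP, PE (mean intensity in the ROI, then weighted by ROI area) | Yes: 7.2.1, 7.2.2; WI/WO also 7.2.3 |
| Choice of parenchyma | PE | Yes: 7.2.1, 7.2.2 |
| Infusion delineation | β, used as WI | Yes: 7.2.2 |
| Echogenicity, shape | Primary model, and the same strategy in 7.2.2 | Yes |
| Qualitative 3D reading | Its own comparison with outcome | No |

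The stage AUCs in 7.2.3 use WI, WO and patient factors. The diagnosis AUCs use the Table 1 factors. The 3D reading is in neither set.

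**3. Is any step protected?** Sections 4.2, 7.2 and 8.3 were read for three things: masking of the reader, an order that puts reading before abstraction, and a lock. None is stated. Coding of images is the nearest safeguard, and it is not said to conceal pathology.

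**4. Illustration of size (the shift d is an assumption).** For a normal score with equal variances, AUC = Φ(δ/√2). A true AUC of 0.80 gives δ = √2 × 0.8416 = 1.190. If knowledge of histology widens the separation by d within-group SDs, AUC = Φ((1.190 + d)/√2). For example, d = 0.3 gives Φ(1.490/1.414) = 0.854.

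The critical value for the one-sided test is 0.80 + 1.645 × 0.0884 = 0.9455.

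| d (SD) | Expected AUC | P(reject AUC ≤ 0.8), normal approx. | Same, 40,000 simulations |
|---|---|---|---|
| 0 | 0.800 | 5.0% | 4.0% |
| 0.1 | 0.819 | 6.7% | 5.8% |
| 0.2 | 0.837 | 8.8% | 8.4% |
| 0.3 | 0.854 | 11.4% | 11.6% |
| 0.5 | 0.884 | 18.1% | 21.0% |

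The illustration treats the score as one fixed variable and leaves aside the model fitting and selection in 7.2.1.

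**The case against.** The best defence is that much of the score leaves a reader little room. Of the 12 factors in Table 1, age, sex and race are not read from images. The TIC metrics average intensity over the whole mass and are weighted by area, so small border changes have limited effect. Histology itself is documented by a pathologist under standard care. The stage objective is conceded in 7.1.2.2 to lack power and serves to inform later studies. All of this stands. It argues for a small bias but does not exclude one, and echogenicity, shape and the reference parenchyma remain open to judgement.

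A reader might also infer several stronger things that the documents do not support:
- **ROIs are hand-drawn.** The text says only that the mass is delineated; manual or automated is not stated.
- **The same small team reads images and abstracts pathology.** This rests on the authors' use of the first person plural. No roles or team size are given.
- **Pathology will normally be known at reading.** Analysis is later, with no date. CEUS may be up to 3 months before surgery, so reading could precede it. Section 8.3 asks for data entry within 5 business days but names neither the trigger nor image metrics, so it is not a lock.
- **B-mode descriptors are scored late.** B-mode is acquired at the CEUS visit; the time of scoring is not stated.
- **The qualitative 3D reading inflates the AUCs.** It enters none.
- **The bias would take up most of the 0.8 to 0.9 effect.** A shift of 0.25 SD gives 0.846, or 0.046 of the 0.10 difference, which is under half. The shift itself has no source in the documents.

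**Conclusion.** The gap is real and should be closed. The plan defers image analysis, obtains histology by chart review, and nowhere masks the reading or fixes its results first. A team could follow it to the letter and read every image with the diagnosis in view. The AUCs in 7.2.1 and 7.2.2 and the WI/WO stage AUCs in 7.2.3 may therefore be too high. The qualitative 3D comparison is exposed separately.

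The size is unknown. Under an assumed shift of 0.1 to 0.5 SD, a true AUC of 0.80 would be estimated at about 0.82 to 0.88, and the chance of wrongly rejecting AUC ≤ 0.8 would rise from about 4% to between about 6% and 21% in simulation. These figures show how sensitive the result is and do not predict the bias. For 7.2.2, each AUC may be raised, but the effect on the bolus-infusion difference cannot be signed.

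**What to change.** Add to 7.2.1, 7.2.2 and 7.2.3 a requirement that, for each subject, the following be completed under the coded ID and locked with a date stamp in REDCap before that subject's pathology is abstracted:
- ROIs, including the parenchyma reference used for PE;
- the TIC metrics derived from them;
- the B-mode descriptors;
- the qualitative 3D reading.

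Withhold the pathology fields from whoever does the reading until the lock. Flag any subject whose images were read after pathology was known. Add a cross-reference in 4.2.3 so that the chart review follows the lock.

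**Cost.** Sample size, alpha, stated power and procedures do not change. REDCap is already the study database, and existing staff can do the work, because the protection comes from the order of the steps. Wholly separate readers could need extra staff and are not required here. The downside is that image analysis must be done promptly after each scan, or pathology abstraction held back, and REDCap access must be set so that pathology fields are hidden before the lock.
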